6.6.2. Bone Mineral Density (BMD) by DXA

BMD of femoral neck, total hip and lumbar spine will be assessed by DXA at Baseline, Month 9 (if required) Month 12 and Month 6 of the extension follow-up (if required). Unacceptable DXA assessments (accepted="No") will not be summarized (hip, spine and femur considered separately).

In case of repeated values due to BMD loss ≥5%, the initial scan will be used in summaries. Initial and repeated scan values will be reported in the listings.

Calibrated values will be used if available, otherwise initial values will be considered.

BMD, expressed as both absolute values and Z-scores will be summarized at each visit in terms of actual values, changes from baseline, changes from baseline 2 (only for the subjects who are

in the placebo arm in the main study) for each anatomic location. For absolute values only, percent change from baseline, percent changes from baseline 2 (only for the subjects who are in the placebo arm in the main study) and 95% confidence interval for the mean percent change from baseline and for the mean percent change from baseline 2 within each group will be produced at each time point.

The definition of both baselines are described in section 6.2.2.

Percent change from baseline and percent change from baseline 2 to Month 9, Month 12 and Month 6 extension follow-up will be described and will also be summarized in categories of percentage with the following classes:

- No change or increase,
- Decrease $\leq 3\%$,
- Decrease > 3% and $\leq 5\%$,
- Decrease > 5% and \leq 7%,
- Decrease > 7% and \leq 8%,
- Decrease > 8%.

All data except unacceptable DXA measurements (accepted="No") will be listed.

Due to the war situation in Ukraine, data from subjects in Ukraine sites may be incomplete, missing or uncleaned. A sensitivity analysis of the BMD will be performed, excluding data collected after 24FEB2022 for subjects from Ukraine sites. An additional listing including subjects from Ukraine only will be provided.

6.6.3. Laboratory Data

Clinical laboratory values will be expressed using conventional SI units.

Hematology, coagulation parameters, chemistry and lipids were assessed at screening and at each visit during the extension treatment period (from M7 to M12), as well as at the M1 ExtFU and M3 ExtFU visits.

E2, progesterone (P4) and LH were assessed at each visit during the extension treatment period (from M6 to M12), as well as at M1 ExtFU and M3 ExtFU visits.

Serum levels of sex hormone-binding globulin (SHBG) were assessed on Month 6, Month 9 and Month 12 visits.

Blood samples were to be analyzed by the central laboratory. Due to the covid-19 situation, some samples may be collected by local laboratories.

For Hematology, coagulation parameters, chemistry and lipids, the actual value, change from baseline and change from baseline 2 (only for the subjects who are in the placebo arm in the

```
CRS-BS-TP-000005 V 2.0
```

main study) will be summarized for each visit for each treatment group. In the event of repeated values, the last non-missing value per study day/time will be used.

Semi-quantitative laboratory results will be imputed as follows: "<X.X" will be imputed as "X.X/2" and ">X.X" will be imputed as "X.X".

Evaluation of shifts for changes from baseline and for changes from baseline 2 (only for the subjects who are in the placebo arm in the main study) to all visits according to the normal ranges with categories "Low", "Normal", "High" where available (for ALT, AST, ALP, Bilirubin, Albumin, Calcium, Creatine Kinase) and according to normal/abnormal/abnormal clinically significant information collected otherwise, will be provided.

For Liver Function Test (LFT) parameters (ALT, AST, ALP, total bilirubin, albumin), evaluation of shifts for changes from baseline will be extended by the worst (highest) on-treatment value (including unscheduled assessments) according to the normal ranges with categories "Low", "Normal", "High" will be provided.

For the lipid panel (Triglycerides, HDL, LDL, Total Cholesterol, LDL/HDL ratio), the percent change from baseline and the percent change from baseline 2 (only for the subjects who are in the placebo arm in the main study) to each on-study visit will also be summarized.

Assessments from local laboratories will not be included in summaries and shift tables, as normal ranges may not be comparable.

For serum levels of E2, P4, SHBG and LH, only the actual values at each time point will be summarized. Note: in the event of repeated values, the last non-missing value per study day/time will be used.

In addition, for E2, the proportion of subjects with the following categories:

- E2 <20 pg/mL,
- E2 between \geq 20 and <60 pg/mL,
- E2 ≥60 pg/mL

at each visit and for each treatment group will be provided in tables and graphically (bar charts).

For E2, samples analysed after the period of long-term stability should be excluded from analysis.

The relationship between E2 serum levels and bone mineral density loss will be explored graphically in different ways:

• First, the E2 serum level measured at Month 12 will be plotted on the x-axis against the percent BMD change from baseline measured at Month 12 on the left side y-axis and the percentage of subjects with clinically meaningful reduction of DYS (resp. NMPP) with stable or decreased use of analgesics for EAP on the right side y-axis. Thresholds from the Month 3 Meaningful Change Threshold analysis will be used for DYS and NMPP. A second plot showing the BMD percent change from baseline 2 (for subjects who are in placebo arm in the main study) and reduction of DYS and NMPP from baseline 2 will be produced.

- Second, bar charts will be produced at each visit from Month 6 to Month 12 and presented with the percent BMD change from baseline to Month 12 on the y-axis and the proportion of subjects with the E2 categories described above on the x-axis. Similar graphs will be produced for each of the BMD sites (femoral neck, hip, and spine), and for the BMD percent change from baseline 2 (for subjects who are in placebo arm in the main study).
- Lastly, bar charts of the proportion of subjects with the E2 categories described above on the x-axis will be plotted against the percentage of responders according to the primary endpoint, using DYS and NMPP thresholds from the Month 3 Meaningful Change Threshold analysis. Bar charts with percentage of responders from baseline 2 will be shown as well.

For P4, since P4 above 10 nMol/L may suggest luteal activity and hence ovulation, the proportion of subjects with P4 >10.0 nMol/L at least once from Month 6 to Month 12 will also be provided in tables.

The number and percentage of subjects with cholesterol values in the following categories

• LDL ≥ 160 mg/dL

Cute CONFIDENTIAL - Kissei

- LDL ≥ 190 mg/dL
- HDL < 40 mg/dL

will be reported at each visit.

Shift tables from baseline and shift tables from baseline 2 (only for the subjects who are in the placebo arm in the main study) to each visit will be provided for the following LDL and Triglycerides categories (after rounding to integer values if necessary).

LDL:

- 0: ≤ 130 mg/dL
- 1: 131 to 159 mg/dL
- 2: 160 to 189 mg/dL
- 3: ≥ 190 mg/dL

Triglycerides:

- 0: ≤ 150 mg/dL
- 1: 151 to 300 mg/dL
- 2: 301 to 500 mg/dL
- 3: 501 to 1000 mg/dL
- 4: >1000 mg/dL

Follicle-Stimulating Hormone (FSH) at local laboratory for subjects that do not resume menses at M3 ExFU visit will be summarized and listed.

All laboratory data will be provided in data listings. Day 1 Serum levels of the anti-müllerian hormone (AMH) and fasting glucose will be included in the listings.

A subset listing will be presented for all abnormal clinically significant laboratory values.

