- IMP accountability based on blisters
- ECG (at about the same time as but before the PK sample)
- Vital signs (blood pressure (BP) and heart rate)
- Urine pregnancy test
- Urinary protein dipstick
- Blood samples for haematology, coagulation parameters, chemistry, hormones (E2, LH and progesterone (P4))
- Pre-dose PK sample (the time of study medication administration on previous 4 days and time of PK sampling will be recorded)
- Contraception dispensing (if applicable) and counselling
- Prescribe/dispense permitted analgesics as rescue medication
- Dispense calcium and vitamin D supplementation

- Dispensing via IWRS of one new kit of linzagolix

The subject will take her daily dose of study medication at the study site from the newly dispensed linzagolix/placebo kit, and from the ABT/placebo kit dispensed at the Month 6 visit.

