- IMP accountability based on blisters
- ECG (at about the same time as but before the PK sample)
- Vital signs (BP and heart rate)
- Urine pregnancy test
- Urinary protein dipstick
- Blood samples (fasting not required) for haematology, coagulation parameters, chemistry, hormones (E2, LH and P4)
- Pre-dose PK sample (the time of study medication administration on previous 4 days and time of PK sampling will be recorded)
- Contraception dispensing (if applicable) and counselling
- Prescribe/dispense permitted analgesics as rescue medication
- Dispense calcium and vitamin D supplementation
- Dispensing via IWRS of one new kit of linzagolix/placebo

The subject will take her daily dose of study medication at the study site from the newly dispensed linzagolix/placebo kit, and from the ABT/placebo kit dispensed at the Month 9 visit.

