10.2.2.1 Study visit: Month 1 Extension FU (Month 1 ExFU)

Month 1 ExFU visit should be scheduled on Day 365 ± 7 days after main study Day 1 (or 28 days ± 7 days after last IMP intake for early discontinued subjects).

The following tests and evaluations will be performed at Month 1 ExFU visit:

- eDiary completion compliance check
- ePRO completion, ideally before any other procedures or assessments: mPGIS and PPGIC (must be completed last)
- Concomitant treatments recording
- AE recording
- Completion of the paper C-SSRS questionnaire (version for “already enrolled subjects” (see Appendix S) for patients responding to the C-SSRS for the first time during the study, or version “since last study visit” (see Appendix T) for patients for whom the C-SSRS was completed at the previous study visit)
- ECG
- Vital signs (BP and heart rate)
- Urine pregnancy test and contraception dispensing and counselling
- Urinary protein dipstick
- Blood samples for haematology, coagulation parameters, chemistry, hormones (E2, LH and P4)
- Endometrial biopsy only if diagnosis at Month 12 was different than “benign endometrium” or if no endometrial biopsy was done at Month 12 (see section 10.4.5).
- Prescribe/dispense permitted analgesics as rescue medication
- Dispense calcium and vitamin D supplementation

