10.4.8 Laboratory parameters

Haematology, coagulation parameters and chemistry will be assessed at each visit during the Treatment Period, as well as at Month 1 ExFU and Month 3 ExFU visits. Fasting lipids will be assessed at Month 9, Month 12 and Month 3 ExFU visits.

E2, P4 and LH will be assessed at each visit during the treatment period, as well as at M1 ExFU and M3 ExFU visits. Serum levels of SHBG will be assessed at Month 9 and Month 12 visits.

Overnight fasting is required for Months 9, 12 and Month 3 ExFU visits.

Blood samples will be analyzed by the central laboratory. Details of blood sampling process, sample handling and shipment are described separately in a laboratory manual provided by the central laboratory. Central laboratory reference ranges will be filed in the investigator site file and in the trial master file. All laboratory results except E2, P4, LH and SHBG levels will be assessed by the Investigator/sub-Investigator. Clinically significant abnormalities compared to main study baseline status will be reported as AEs in the eCRF. E2, P4, LH and SHBG levels will not be communicated to keep the operational team and the sites blinded to treatment administration.

The laboratory parameters are listed in Appendix M.

There may be some additional laboratory parameters to be analysed as requested by the medical monitor in order to follow-up on existing abnormalities.

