Appendix A. Schedule of study assessments – Treatment Period

Schedule of study assessments – Treatment Period							
Timing ¹	Treatment Period						
	M6 ²	M7	M8	M9	M10	M11	M12
Informed Consent	X						
Inclusion-Exclusion criteria	X						
Physical examination (including weight)	X			X			X
Columbia-Suicide Severity Rating Scale	X	X	X	X	X	X	X
ECG ³	X	X	X	X	X	X	X
Vital signs	X	X	X	X	X	X	X
Urine pregnancy test	X	X	X	X	X	X	X
Endometrium TVUS	X			X			X
Gynecological examination	X			X			X
Endometrial biopsy	X ⁴						X ⁴
Manual breast examination	X						X
Clinical laboratory & urinary protein dipstick	X ⁵	X	X	X ⁵	X	X	X ⁵
BMD by DXA	X			X ⁶			X
Adverse events	X	X	X	X	X	X	X
Concomitant medication	X	X	X	X	X	X	X
Contraceptive dispensing and counselling	X	X	X	X	X	X	X
Permitted analgesic prescribing/dispensing	X	X	X	X	X	X	X
Vitamin D and calcium dispensing	X	X	X	X	X	X	X
Subject eDiary completion check	X	X	X	X	X	X	X

¹ All visits should take place at the end of the defined period (i.e. M7 visit should be scheduled at the end of Month 7, M8 visit should be scheduled at the end of Month 8, etc.). All visit dates should be calculated from the date of Day 1 visit (in the main study). A month is defined as 28 days/4 weeks. Visits should be scheduled ± 3 days (-3/+ 2 days for Month 7 visit) from the calculated date.

² All Month 6 assessments except informed consent and inclusion/exclusion criteria would have been performed as part of the main study (18-OBE2109-003 - Edelweiss 3).

³ ECG should be performed at about the same time but before the PK sample

⁴ If endometrium thickness in TVUS is ≤ 5 mm, no endometrial biopsy will be necessary.

⁵ Overnight fasting is required.

⁶ Only for subjects who met the following criterion at any site on the M6 DXA scan: $-2.5 < Z\text{-score} \leq -1.5$

Schedule of study assessments – Treatment Period (cont'd)

Schedule of study assessments – Treatment Period							
Timing ¹	Treatment Period						
	M6 ²	M7	M8	M9	M10	M11	M12
IMP accountability	X	X	X	X	X	X	X
Dispense linzagolix/placebo kit	X	X	X	X	X	X	
Dispense ABT/placebo kit	X			X			
EHP-30, EQ-5D-5L and PROMIS ³	X	X		X			X
mPGIS, PGIC, HRUQ and HRPQ ³	X	X	X	X	X	X	X
SSIQ and PSIQ ³	X						X
Blood sample for PK ⁴	X	X	X	X	X	X	X
E2, LH, P4	X	X	X	X	X	X	X
SHBG	X			X			X
Bone biomarkers	X			X			X

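### Glucose change is to be summarised at every chemistry visit although fasting is required at only some of them, so placebo switchers may show a spurious rise against Baseline 2 as linzagolix starts

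*SAP*

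**What the plan says.** Protocol Appendix M lists glucose under blood chemistry. On timing, protocol 10.4.8 says: "Haematology, coagulation parameters and chemistry will be assessed at each visit during the Treatment Period", and adds Month 1 and Month 3 ExFU. On fasting, the same section says: "Overnight fasting is required for Months 9, 12 and Month 3 ExFU visits". Month 6 is added by footnote 5 on the clinical laboratory row of Appendix A ("Overnight fasting is required").

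For the remaining visits:
- Months 10 and 11 (protocol 10.2.1.4): "Blood samples (fasting not required) for haematology, coagulation parameters, chemistry, hormones (E2, LH and P4".
- Months 7 and 8 (protocol 10.2.1.2): "Blood samples for haematology, coagulation parameters, chemistry, hormones (E2, LH and progesterone (P4", with no word on fasting.
- Month 1 ExFU (protocol 10.2.2.1): "Blood samples for haematology, coagulation parameters, chemistry, hormones (E2, LH and P4", again with no word on fasting.

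SAP 6.6.3 takes "For Hematology, coagulation parameters, chemistry and lipids, the actual value, change from baseline and change from baseline 2" and summarises them at each visit in each group, with Baseline 2 used only for subjects on placebo in the main study. It has no restriction, stratification or flag by fasting status. Fasting glucose is mentioned there once, as a Day 1 value alongside anti-müllerian hormone: "and fasting glucose will be included in the listings". SAP 6.2.2 defines Baseline 2 as the last assessment before the first active dose in the extension. It refers the main baseline to the main-study SAP.

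**The concern.** Glucose depends on whether the subject has eaten. A change score that subtracts a fasting value from a value with uncontrolled fasting status mixes the effect of a meal with the effect of treatment. Here the mismatch falls at an awkward time: the placebo switchers' first two visits on linzagolix, with or without add-back therapy, are visits without required fasting, and their reference value is a fasting one. A reader of the table could take the difference for an early metabolic effect. No group stays on placebo in the extension, so no concurrent control would move in parallel and expose it. Laboratory change from baseline is a named safety endpoint (protocol 7.2), and within-group change by visit is the form in which it will be reported.

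**Working it through.** The documents state no figure for glucose or for a fasting effect, so there is nothing to reproduce. The check is a visit map followed by an illustration of size.

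**Visit map** (chemistry visits; Month 6 ExFU has no chemistry)

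| Visit | Fasting | Change from Baseline 2 in placebo switchers |
|---|---|---|
| Month 6 | required (Appendix A, footnote 5) | reference value |
| Months 7, 8 | no instruction | fasting status not matched |
| Month 9 | required | like for like |
| Months 10, 11 | stated as not required | not matched |
| Month 12 | required | like for like |
| Month 1 ExFU | no instruction | not matched |
| Month 3 ExFU | required | like for like |

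Chemistry visits after Month 6: 8. Fasting required at 3 (Months 9, 12, Month 3 ExFU). Not required at 8 − 3 = 5, and 5/8 = 63%.

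Baseline 2 is normally the Month 6 sample. Protocol 10.1 and 10.2.1.1 place consent and the first extension dose after the Month 6 assessments, so that sample is the last one before active drug.

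**Possible size.** Let f be the share of subjects who ate before a visit without required fasting, and d the mean fed-minus-fasting difference in glucose. The artefact in mean change from Baseline 2 is f × d. Both inputs are assumptions:
- f = 0.25, d = 0.3 mmol/L: 0.075 mmol/L
- f = 0.5, d = 0.6 mmol/L: 0.30 mmol/L
- f = 1.0, d = 1.0 mmol/L: 1.0 mmol/L

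**Set against sampling error.** Expected entry is 450 × 0.80 × 0.80 = 288, which agrees with protocol 13.2. If entry is equal across the three main-study arms and the placebo arm splits 1:1, each placebo-switch group has 288/3/2 = 48 subjects. With an assumed SD of change of 0.6 to 1.0 mmol/L, the standard error of the mean change is 0.6/√48 = 0.087 to 1.0/√48 = 0.144 mmol/L. The artefact then runs from 0.075/0.144 = 0.5 to 1.0/0.087 = 11.5 standard errors. The middle case gives 0.30/0.144 = 2.1 to 0.30/0.087 = 3.4. It could therefore be lost in noise or be plainly visible.

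**After the fix.** At the fasting-required visits with a fasting reference, f × d does not enter, provided subjects followed the fasting instruction.

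**Two side checks**
- Withdrawal visits follow the Month 12 procedures (protocol 10.7.2), which include fasting blood. SAP 5.5 assigns early-discontinuation safety data to the scheduled visit within 14 days if that assessment was planned there. A fasting withdrawal value can therefore land in, say, the Month 8 or Month 10 row, mixing fasting states within one visit.
- SAP 6.6.3 says lipids were assessed at each visit from Month 7 to Month 12 and at Months 1 and 3 of follow-up. Protocol 10.4.8 has them only at Months 9, 12 and Month 3 ExFU.

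**The case against.** The strongest reply is that the consequence is small. The summaries are descriptive and no hypothesis is tested. All four groups share the visit schedule, so comparing groups at a given visit is unaffected. Glucose is neither a named endpoint in its own right nor a discontinuation criterion. The same table has matched Baseline 2 comparisons at Months 9, 12 and Month 3 ExFU, where a sustained effect would show. A footnote might be enough. All of this stands, and it limits the point to an inexpensive repair. It does not remove it, because within-group change by visit is exactly what is planned.

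Four stronger readings are tempting, and the documents do not support them:
- **That the five visits are non-fasting.** The protocol says not required at two of them and is silent at three. Some subjects may have fasted anyway, so a rise is possible rather than certain.
- **That change from the main-study baseline carries the same mismatch.** The SAP mentions a Day 1 fasting glucose only for listings, says chemistry was taken at screening, and defers the baseline definition to a document not available here. If that baseline was not fasting, the mismatch would fall on the fasting visits instead.
- **That glucose appears to rise at linzagolix onset in general.** The continuing groups started linzagolix six months earlier. Onset concerns only the placebo switchers, about 2 × 48 = 96 of 288 under equal entry.
- **That the lipid sentence adds non-fasting lipid results.** The protocol schedules no lipids at those visits, so this is a conflict of wording.

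**Conclusion.** The point holds as a predictable weakness in one safety summary. Followed as written, the SAP compares a fasting Month 6 value with samples not required to be fasting at the placebo switchers' first two linzagolix visits, and again at Months 10, 11 and Month 1 ExFU. By-visit glucose may swing on the same schedule in all four groups, whatever the fasting status of the main baseline. The visit map rests on the documents alone. The size does not: 0.075 to 1.0 mmol/L depends on an assumed fed share of 0.25 to 1.0 and an assumed meal effect of 0.3 to 1.0 mmol/L. The SAP already applies the underlying principle elsewhere in 6.6.3, where local-laboratory results are kept out of the summaries because their normal ranges may not be comparable. The change is worth making because it is cheap; no efficacy conclusion depends on it.

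**What to change.** In SAP 6.6.3:
1. Summarise glucose change from baseline, change from Baseline 2 and shifts only at the fasting-required visits: Months 6, 9, 12 and Month 3 ExFU. Glucose is not among the parameters named for low/normal/high shifts, so the restriction applies to its normal/abnormal shifts.
2. Use a fasting reference value. For Baseline 2 this is the Month 6 sample. For the main baseline, use the Day 1 fasting glucose if it is confirmed to be one; otherwise say that the fasting status of the baseline is unknown.
3. List glucose from Months 7, 8, 10, 11 and Month 1 ExFU, or show actual values only, labelled as fasting not required.
4. Include withdrawal-visit glucose in the change summary only if fasting status is recorded. The documents do not show that it is.
5. Align the sentence on lipid timing with protocol 10.4.8 (Months 9, 12 and Month 3 ExFU). This is a minor wording correction.

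The cost is a few lines of SAP text and a visit filter, with no new data. The loss is the glucose change summary at five visits, where the change cannot be interpreted as it stands.

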Liver function tests: following the Food and Drug Administration (FDA) guidance on drug-induced liver injury (8), subjects who have an elevation of hepatic enzymes are to be withdrawn immediately from treatment if:

- ALT or AST $>8xULN$
- ALT or AST $>5xULN$ for more than 2 weeks
- ALT or AST $>3xULN$ and (TBL $>2xULN$ or INR >1.5)
- ALT or AST $>3xULN$ with the appearance of fatigue, nausea, vomiting, right upper quadrant pain or tenderness, fever, rash, and/or eosinophilia ($>5\%$)

Withdrawn subjects will be followed up until hepatic parameters return to normal.

ECG: subjects who have a QTcF > 500 ms or increase > 60 ms from the highest value prior to the first dose in the main study will have to be withdrawn from study treatment and followed up until return to QTcF < 480 ms or – if not reached after 3 months of treatment cessation- be referred to a cardiologist. They will enter the 6-month Follow-Up Period and undergo the follow-up ECGs according to the schedule of events.

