7. CHANGES TO PLANNED ANALYSES

The Follow-up Extension Analysis Set, defined in protocol as:

All subjects from the main study who completed the 6 months of treatment in the extension study and who entered the Post-Treatment Follow-Up Period. Subjects will be analyzed according to randomized treatment.

Is changed to:

All subjects from the main study who entered the extension study and received at least one dose of study drug with the exception of subjects whose Month 6 assessment subsequently met any of the discontinuation criteria, and who entered the Post-Treatment Follow-Up Period. Subjects will be analyzed according to randomized treatment.

The rationale for this modification is that subjects that entered the Follow-up period, even if they did not complete the 6 months of extension treatment should be followed up for efficacy.

SAP Version	Update description	SAP Section	Reason
V2.0	Assessments from Local Laboratories (due to Covid-19 situation) will be excluded from summary tables of laboratory data	Section 6.6.3	Local laboratories may not have comparable normal ranges, thus it does not make sense to pool them with central laboratory data in numeric summaries.
V2.0	Biopsy assessments from Local Laboratories (due to war situation in Ukraine) should be flagged in listings. Information is available in Data Management Closed Queries File.	Section 6.6.8.1	Due to war situation in Ukraine, there were some Biopsies assessed locally. This information should be incorporated in listings.
V2.0	Addition of listings for PAP Smear for both abnormality and diagnosis information.	Section 6.6.8.3	PAP Smear listings were missing from original SAP Version.
V3.0	All protocol deviations related to a particular subject will be presented in the data listings.	Section 4.2	There were PD records which had missing subject ID and thus were not

Updates from SAP Amendments since SAP V1.0 are summarized in the table below:

CRS-BS-TP-000005 V 2.0

Page **75** of **99**

Kissei / Cytel Confidential: This is a controlled document and shall not be changed, saved, copied or reproduced by any unauthorized person.

			related to any particular subject. These records were excluded in the listings.

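### The worst-value liver shift takes the highest albumin as worst, and no table counts women who reached the protocol's ALT/AST thresholds on extension treatment

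*SAP*

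**What the plan says.** SAP 6.6.3 plans Low/Normal/High shift tables from baseline to every visit for ALT, AST, ALP, bilirubin, albumin, calcium and creatine kinase. It then adds a worst-value analysis for a named liver panel of ALT, AST, ALP, total bilirubin and albumin, where the shift evaluation "will be extended by the worst (highest) on-treatment value (including unscheduled assessments"), again in Low/Normal/High. Albumin is on that list with no exception; INR is not on it.

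On local laboratories, the same section notes that "Due to the covid-19 situation, some samples may be collected by local laboratories", and then rules: "Assessments from local laboratories will not be included in summaries and shift tables, as normal ranges may not be comparable". The amendment table in SAP 7 gives the same concern about normal ranges and concludes that "it does not make sense to pool them with central laboratory data in numeric summaries".

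Protocol 10.7.2.1 works in multiples of ULN: "subjects who have an elevation of hepatic enzymes are to be withdrawn immediately from treatment if" any one of these holds: ALT or AST exceeds 8xULN, exceeds 5xULN for over two weeks, or exceeds 3xULN together with total bilirubin above 2xULN, INR above 1.5, or listed symptoms or eosinophilia. SAP 4.1 programmes these same criteria at Month 6 to define the Treatment Extension Analysis Set, and SAP 6.3.1 counts women meeting any Month 6 discontinuation criterion.

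**The concern.** A worst-value table exists to show each woman's most adverse result. One direction for all five parameters cannot do that, because enzymes and bilirubin are adverse when they rise and albumin is adverse when it falls.

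The second gap is one of resolution. Raised transaminases are a recognised risk in Protocol 5.7 and carry their own withdrawal criteria, and Protocol 5.5.3 describes earlier studies in multiples of ULN (some values above 3xULN; none above 2xULN in the Phase 2b extension). A Low/Normal/High table cannot be compared with either. The SAP does grade other safety data: BMD loss up to its own 8% limit in 6.6.2, and LDL and triglycerides in 6.6.3.

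Third, leaving local results out of the shift tables sits awkwardly with a worst-value analysis that is meant to include unscheduled assessments. At stake is the incidence by treatment group that a reader of the study report can take from the tables.

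**Working it through.** **1. Albumin.** Scheduled chemistry at Months 7 to 12 gives six on-treatment values. The highest of six is Low only if all six are Low. With five low and one normal, the worst-value entry is Normal, while the by-visit shifts show Low at five visits. A second illustration uses 42, 40, 28, 36, 41 and 42 g/L with an assumed range of 35 to 50:

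- highest = 42, classified Normal (the SAP rule);
- lowest = 28, classified Low.

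**2. Enzyme categories.** With the cut at 1xULN:

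| ALT (xULN) | Category in SAP 6.6.3 | Protocol threshold exceeded |
|---|---|---|
| 1.2 | High | none |
| 3.1 | High | >3x |
| 5.1 | High | >5x |
| 8.1 | High | >8x |

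All four share one cell. This holds even if every sample is central. The >3x criterion acts only with a bilirubin, INR or clinical finding, and the >5x criterion only with duration; no planned laboratory table combines these.

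**3. Local results.** The plan's enrolment figure reproduces: 450 x 0.80 = 360, and 360 x 0.80 = 288. Neither the local share f nor the event rate r is given, so both are assumed, with one qualifying sample per event and local status independent of the event.

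- Expected events lost = 288 x r x f
- Chance of losing at least one = 1 - (1 - r x f)^288

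| r | f | Expected lost | Chance of at least one |
|---|---|---|---|
| 0.5% | 1% | 0.014 | 1.4% |
| 1% | 10% | 0.288 | 25.0% |
| 2% | 20% | 1.152 | 68.5% |

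The range is too wide to fix a size. If retests of raised values are more often local, the loss is larger. If a woman also has a qualifying central value, she is not lost at all.

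**4. Where such events do appear.** SAP 6.6.3 lists all laboratory data, plus a subset listing of clinically significant abnormal results, with no local exclusion stated for either. SAP 6.6.1 counts and lists TEAEs leading to permanent discontinuation. Under Protocol 12.1.2, an abnormality that ends IMP meets a condition for AE reporting. Protocol 5.7 gives the DMC regular sight of transaminases. None of these yields a rate by group at a fixed multiple of ULN.

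**The case against.** A reader might infer that these tables could make the trial miss the liver events its stopping rules are meant to catch. The documents do not support that. The rules act on each woman during treatment, not through final tables. Albumin is in none of them, so the albumin wording cannot hide such an event. The routes in step 4 also remain open.

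A reader might also put a rate on the local exclusion: 288/3 = 96 women per continuing group (assuming equal retention), so each locally measured ALT peak would cost 1/96, about 1.0 percentage point. That does not follow. In a Low/Normal/High table she still counts as High if any central on-treatment value exceeds ULN, and chemistry is drawn at every treatment visit. An incidence above 3xULN cannot be understated in a table that is not planned.

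The exclusion itself is defensible in part. With a central baseline and a local follow-up, a move from Normal to High may reflect a different range rather than a change in the patient. The SAP 7 rationale does open with normal ranges, so I do not treat it as contradicting 6.6.3. Its conclusion, however, concerns numeric pooling. A shift table can classify each value against the range of the laboratory that measured it, and the SAP itself summarises locally measured FSH.

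Local ranges cannot be presumed to be in the database. Protocol 10.4.8 mentions filing central ranges only, and the flagging of local assessments in SAP 6.6.8.1 concerns biopsies, not chemistry. That objection stands and limits the fix. It is also true that the study is descriptive and that neither document promises a table in multiples of ULN, so its absence is a gap to improve on rather than a broken commitment.

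**Conclusion.** The albumin direction is wrong as written. Its reach is one entry per woman in the worst-value shift, since by-visit shifts still show low albumin.

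The missing threshold table is a worthwhile and cheap improvement. As planned, no table shows how many women on extension treatment reached the ALT/AST levels at which the protocol acts. This conclusion needs no assumption about local samples.

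The local-laboratory effect is real in direction but of unknown size. The 0.014 to 1.15 events in step 3 rest entirely on assumed rates and shares, and 288 is itself a planning maximum. The documents do not support a flat statement that liver abnormality will be understated by a given amount.

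**What to change.** In SAP 6.6.3:

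- (a) Define worst on-treatment as the highest value for ALT, AST, ALP and total bilirubin, and the lowest for albumin.
- (b) Add one worst on-treatment table by treatment group: ALT or AST above 3x, 5x and 8xULN, and above 3xULN with total bilirubin above 2xULN or INR above 1.5. The Month 6 criteria programming behind SAP 4.1 can be reused. The 5x row would count peak values, without the protocol's duration condition.
- (c) Where a local laboratory's range is in the database, include its results in the worst-value and ULN-multiple tables as multiples of that laboratory's ULN, and give a central-only version as a sensitivity analysis. Keep local results out of numeric means. State how many samples were local and how many lacked a range.

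The cost is a few words for (a), one table for (b), and for (c) a check of which local ranges are held, plus the central-only version. The downside is that liver results may look slightly less favourable. No withdrawal criterion or other clinical rule changes.
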